**Table 11-5    Acceptable Methods of Contraception**

Method	Male Subjects and Their Female (Non-study) Partners	Female Subjects and Their Male (Non-study) Partners
Vasectomy 6 months or more previously, with a documented negative postvasectomy semen analysis for sperm	Yes	Yes
Documented bilateral tubal ligation performed at least 6 months previously	Yes	Yes
Male or female condom with or without spermicide a	Yes	Yes
Female barrier contraception (such as diaphragm, cervical cap, or sponge) with spermicide	Yes	Yes

**Table 11-5 Acceptable Methods of Contraception**

Method	Male Subjects and Their Female (Non-study) Partners	Female Subjects and Their Male (Non-study) Partners
Continuous use of a non-hormone releasing intrauterine device for at least 90 days before the dose of study drug	Yes	Yes
Oral, patch, implanted, injected hormonal contraceptives, if used consistently and correctly for at least 60 days before the dose of study drug	Yes	No

Note: At least 1 acceptable method of contraception must be used by couples not exempt from the contraception requirement.

a A female condom cannot be used with a male condom due to risk of tearing.

#### **Additional notes:**

- Male and female subjects who are not sexually active at the time of screening must agree to follow the contraceptive requirements of this study if they become sexually active with a partner of the opposite sex.
- Male subjects must not donate sperm during the period starting from the dose of study drug until 90 days after the dose of study drug.
- Female subjects of childbearing potential should not plan to become pregnant during the study or within 90 days after the dose of study drug. For male subjects with a female partner of childbearing potential, the couple should not plan to become pregnant during the study or within 90 days after the dose of study drug, with the exception of couples who plan to become pregnant by artificial insemination using sperm banked by the male subject before the dose of study drug or sperm from another source.
- Male subjects whose female partner becomes pregnant through well-documented in vitro fertilization (donated sperm) or banked sperm (collected before the subject received study drug), or is otherwise already pregnant before the male subject's dose of study drug, must be compliant with the contraception requirements. In this scenario, the male subject and his female partner must commit to using a male condom (to ensure there is no exposure of the fetus to study drug) from signing consent through 90 days after the dose of study drug.
- Female subjects should not nurse a child from signing consent through 90 days following the study drug administration.
- Unique situations that may not fall within the above specifications may be discussed with the Vertex medical monitor or authorized designee on an individual basis.

#### **11.6.8.2 Pregnancy**

Subjects will be counseled to inform the investigator of any pregnancy that occurs during study treatment and for 90 days after the last dose of study drug.

If a subject or the female partner of a male subject becomes pregnant while participating in the study, study drug will be permanently discontinued immediately. The investigator will notify the medical monitor and Vertex Global Patient Safety (GPS) within 24 hours of the site's knowledge of the subject's (or partner's) pregnancy using the Pregnancy Information Collection Form.

[figure not shown]
A subject (or their partner, if relevant) who becomes pregnant within 90 days after the last dose of study drug will be followed until the end of the pregnancy. The infant will be followed for 1 year after birth, provided informed consent is obtained. A separate ICF will be provided to explain these follow-up activities. Pregnancy itself is not an AE.

## 12 STATISTICAL ANALYSIS

This section presents a summary of the principal features of the planned efficacy and safety analyses for the study. Efficacy and safety analysis details will be provided in the statistical analysis plan (SAP), and [REDACTED]

[REDACTED] Both the SAP and [REDACTED] will be finalized before the clinical data lock. [REDACTED]

Final analyses will take place after all subjects have completed the study, all data have been entered in the clinical study database, and the clinical data have been locked.

### 12.2 Analysis Sets

The **All Subjects Set** is defined as all subjects who were enrolled or received at least 1 dose of study drug. This analysis set will be used for individual subject data listings and disposition summary tables unless otherwise specified.

The **Full Analysis Set (FAS)** is defined as all enrolled subjects who have received at least 1 dose of study drug. The FAS will be used to summarize background characteristics and for all efficacy analyses unless otherwise specified.

The **Safety Set (SS)** is defined as all subjects who have received at least 1 dose of study drug. The SS will be used for all safety analyses unless otherwise specified.

## 12.3 Statistical Analysis

### 12.3.1 General Considerations

All individual subject data for subjects who were enrolled or received at least 1 dose of study drug will be presented in individual subject data listings. Data from Groups A and B will be pooled for the analysis of endpoints collected in both groups, unless specified otherwise.

**Continuous variables** will be summarized using the following descriptive summary statistics: the number of subjects (n), mean, SD, median, minimum value (min), and maximum value (max).

**Categorical variables** will be summarized using counts and percentages.

**Baseline value**, unless specified otherwise, will be defined as the most recent non-missing measurement (scheduled or unscheduled) collected before the first dose of study drug. For ECGs, the baseline value will be defined as the average of the non-missing pretreatment measurements (triplicate) on Day 1.

**Change (absolute change) from baseline** will be calculated as Post-baseline value – Baseline value.

**Treatment-emergent (TE) Period** will include the time from the first dose of study drug to 28 days after the last dose of study drug or to the completion of study participation (as defined in Section 9.1.9), whichever occurs first.

### 12.3.2 Background Characteristics

Subject disposition (e.g., enrolled, completed treatment, discontinued treatment) will be summarized based on the All Subjects Set.

Demographics (e.g., age) and background characteristics (e.g., blood levels of antigenic AAT at screening, prior augmentation therapy, Z-polymer accumulation in the liver at baseline in Group B), will be summarized. Also, medical history and medication use will be summarized descriptively.

Exposure to study drug (i.e., duration of treatment) will be summarized based on the SS. Study drug compliance (i.e., percentage of days without study drug interruption) will be summarized based on the FAS.

Important protocol deviations will be provided in an individual subject data listing, and summarized, as appropriate.

Additional details will be provided in the SAP.

### 12.3.3 Efficacy Analysis

Only the principal features of the efficacy analysis will be presented in this section. For more details, refer to the SAP.

#### 12.3.3.1 Analysis of Primary Endpoint

The primary efficacy endpoint is the change from baseline in blood levels of functional AAT at Week 48.

The primary analysis will be based on a mixed-effects model for repeated measures (MMRM) with change from baseline in blood levels of functional AAT as the dependent variable. The

model will include visit as a fixed effect. The model will be estimated using restricted maximum likelihood. Denominator degrees of freedom for the *F*-test for fixed effects will be estimated using the Kenward-Roger approximation. An unstructured covariance structure will be used to model the within-subject errors. If the model estimation does not converge, a compound symmetry covariance structure will be used instead.

The primary result obtained from the model will be the estimated change from baseline in blood levels of functional AAT at Week 48 and the corresponding 95% CI and *P* value for the within-group comparison.

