a If serum chemistry was completed more than 28 (+7) days before Day 1 dosing, the LFT panel must be completed within 28 (+7) days before Day 1 dosing.

b Pretreatment liver biopsy must be performed at least 7 days before Day 1 dosing.

**Assessments** **Efficacy:** Blood samples for levels of functional AAT, antigenic AAT, and Z-polymer, and liver biopsy (to evaluate Z-polymer accumulation in the liver)  
**Safety:** AEs, clinical laboratory assessments, standard 12-lead ECGs, clinical evaluation of vital signs, and physical examinations

**Statistical Analyses** The primary efficacy endpoint is the change from baseline in blood levels of functional AAT at Week 48.

Assuming (1) the mean of blood levels of functional AAT at baseline is 4.1  $\mu$ M (SD of 0.6  $\mu$ M); (2) post-baseline blood levels of functional AAT have a constant coefficient of variation of 0.25; and (3) an intra-subject correlation of 0.8 between baseline and post-baseline measurements, the 95% CI for the change from baseline in blood levels of functional AAT at Week 48 has a half-width between 0.59 and 1.24 if the observed change from baseline is between 2 and 7  $\mu$ M with a sample size of 16 evaluable subjects (combining Groups A and B). To account for up to a 20% dropout rate, 20 subjects will be enrolled.

The primary analysis will be based on a mixed-effects model for repeated measures (MMRM) with change from baseline in blood levels of functional AAT as the dependent variable. The model will include visit as a fixed effect.

Interim analyses may be conducted at the discretion of the sponsor.

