#### **9.8            Study Drug Interruption and Stopping Rules**

The medical monitor should be notified of an interruption of study drug for any reason and of the resumption of study drug after such interruption.

The investigator has the discretion to discontinue study drug treatment at any time if the investigator feels that the subject's continued participation in the study jeopardizes the subject's safety.

Any subject with worsening of AATD or disease progression that, in the judgement of the treating physician, requires (re)initiation of standard of care treatment (per local guidelines) that is prohibited in this study (including AAT augmentation therapy) will discontinue study drug treatment, and will be discontinued from the study.

Any subject with QTcF values above the threshold values as described in Section 11.6.5 will discontinue study drug treatment.

On Day 1, urine and serum beta-human chorionic gonadotropin ( $\beta$ -hCG) tests will be performed and subsequently every 4 weeks, continuing through completion of study participation, a urine  $\beta$ -hCG test will be performed. If a urine pregnancy test is positive, all study drug dosing will stop, and the pregnancy will be confirmed with a serum  $\beta$ -hCG test. If pregnancy is confirmed, the procedures outlined in Section 11.6.8.2 will be followed.

Study drug treatment may be interrupted for safety concerns at discretion of the investigator.

Study drug administration must be interrupted immediately (before confirmatory testing), and the medical monitor must be notified, if any of the following criteria are met:

- ALT or AST  $>5 \times$  ULN
- Total bilirubin  $>3 \times$  ULN
- ALT or AST  $>3 \times$  ULN associated with total bilirubin  $>2 \times$  ULN and/or clinical jaundice

Subjects with new treatment-emergent ALT or AST elevations of  $>3 \times$  ULN, or total bilirubin  $>2 \times$  ULN, must be followed closely, including confirmatory testing performed within 2 to 3 days of the initial finding and there must be close monitoring of ALT, AST, and bilirubin levels thereafter, as clinically indicated.

If a subject cannot return to the site for confirmatory testing, a local laboratory may be used. Local laboratory results must be reported immediately to the medical monitor, and the subject must have the tests repeated and sent to the central laboratory as soon as possible (ideally within 2 to 3 days).

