### **12.3.3.4 Missing Data Handling**

For the primary analysis, missing data will be assumed to be missing at random conditional on the observed data; consequently, no imputation of missing data will be performed.

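### The primary MMRM leaves out baseline functional AAT, so it relies on a narrower missing-at-random assumption than the protocol states and would overstate the Week 48 change if low-baseline subjects left very early

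*Protocol*

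**What the plan says.** Protocol 12.3.3.1, repeated in the synopsis, specifies an MMRM "with change from baseline in blood levels of functional AAT as the dependent variable". The "model will include visit as a fixed effect"; no other term is listed. On covariance it says: "An unstructured covariance structure will be used to model the within-subject errors", with compound symmetry if the fit does not converge. The result is the estimated Week 48 change with its 95% CI and P value.

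Protocol 12.3.3.4 says that "missing data will be assumed to be missing at random conditional on the observed data; consequently, no imputation of missing data will be performed".

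Baseline is drawn on Day 1 (Table 3-3). Functional AAT is then scheduled at 13 on-treatment visits, from Day 7 to Week 48 (Tables 3-3 and 3-4; SAP Table 12-1). Protocol 9.8 takes off treatment and out of the study any subject whose worsening disease calls for prohibited standard-of-care treatment, including augmentation.

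Protocol 12.3.3 gives principal features only and refers to the SAP. SAP 9.3.1 is blacked out after its reference to protocol version 2.0. SAP 3.1 lists no modification to the protocol. SAP 9.3.2 makes the secondary blood endpoints descriptive.

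**The concern.** Because the response is the change, baseline is neither a covariate nor a response. Two subjects with the same earlier changes but different baselines are treated as exchangeable when one of them drops out. The likelihood is valid if dropout depends on observed changes. It is not valid in general if dropout also depends on baseline, although baseline is observed. That is a narrower condition than the observed data named in 12.3.3.4.

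This matters only if baseline predicts the change and also predicts who leaves. The planning assumptions imply the first. Protocol 9.8 makes the second plausible. With no control arm, nothing cancels the resulting shift in the estimate.

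**Working it through.** **Inputs (synopsis, Statistical Analyses).** Baseline mean 4.1 µM, SD 0.6; post-baseline "constant coefficient of variation of 0.25"; baseline to post-baseline correlation 0.8; 16 evaluable of 20 enrolled.

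**1. Reproduce the plan's figure.** SD_post = 0.25 × (4.1 + change), which is 1.525 at +2 and 2.775 at +7.
Var(change) = 0.6² + SD_post² − 2 × 0.8 × 0.6 × SD_post.
- At +2: 0.36 + 2.326 − 1.464 = 1.222, SD 1.105. Half-width = 2.131 × 1.105/√16 = 0.589.
- At +7: 0.36 + 7.701 − 2.664 = 5.397, SD 2.323. Half-width = 2.131 × 2.323/√16 = 1.238.

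These match the stated 0.59 and 1.24.

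**2. Slope of change on baseline** = 0.8 × SD_post/0.6 − 1.
- At +2: 2.033 − 1 = +1.03; correlation 1.03 × 0.6/1.105 = 0.56; R² 0.31.
- At +7: 3.70 − 1 = +2.70; correlation 2.70 × 0.6/2.323 = 0.70; R² 0.49.

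At +2 the slope would turn negative only if the correlation were below 0.6/1.525 = 0.39.

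**3. Loss before any post-baseline sample.** If the lowest 20% of a normal baseline leave, the mean baseline of those who remain rises by 0.35 × 0.6 = 0.21 µM. The large-sample bias is 0.21 × 1.03 = +0.22 µM at +2 and 0.21 × 2.70 = +0.57 µM at +7. Simulated with 20 subjects and the four lowest leaving, it is +0.21 and +0.54. That is 35% and 44% of the half-widths, and CI coverage falls to 87% and 82%. With four leaving at random, bias is 0.00 and coverage 95%.

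**4. Loss later, on the 13-visit schedule.** This used simulation with 20 subjects, four dropouts and an unstructured covariance. Two inputs are assumptions because the documents do not give them: the correlation between post-baseline visits (0.65 to 0.9) and the dropout mechanism (the four lowest baselines leave, or the chance of leaving rises as baseline falls).

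| When the low-baseline subjects leave | Bias at +2 (µM) | Bias at +7 (µM) |
|---|---|---|
| Before any post-baseline sample | about +0.2 | about +0.5 |
| After the first visit (Day 7) | +0.04 to +0.16 | +0.11 to +0.32 |
| Spread over the visits | 0.00 to +0.07 | −0.01 to +0.11 |
| Random dropout | nil | nil |

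The bias fades because earlier changes carry much of the information in baseline, and more so as the inter-visit correlation rises.

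**5. Effect of adjusting.** A single baseline main effect removed most or all of the baseline-driven bias on this schedule. RMSE was lower than, or within about 4% of, that of the visit-only model. A baseline-by-visit term raised RMSE in every spread-exit case, for example from 0.296 to 0.333.

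**6. Keeping the interval honest.** At +2 the residual SD is 0.915. Treating the mean baseline as fixed gives a half-width of 2.145 × 0.915/4 = 0.49, which is too narrow. Adding the sampling variance of the mean baseline of 20 subjects, 1.033² × 0.36/20 = 0.0192, gives SE = √(0.0523 + 0.0192) = 0.267. This agrees with the simulated 0.268. The half-width becomes 2.145 × 0.267 = 0.57, close to the planned 0.59.

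**The case against.** The strongest reply is that the effect is small on the trial's real schedule. Functional AAT is first drawn after baseline on Day 7 and at 12 visits after that, so a subject must leave almost at once for baseline to matter much. That stands: with spread exits the bias is at most about +0.1 µM.

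A second reply is that the dropout route is conjecture. Protocol 9.8 is triggered by clinical worsening, not by a low baseline. Functional AAT is withheld from sites (Protocol 10.7), and exclusion criterion 5 keeps out subjects for whom stopping augmentation is not in their best interest. That also stands. A reader might infer that low-baseline subjects did leave first and that the trial's estimate is inflated; nothing in the documents shows this.

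A third reply concerns model size. Thirteen visits already need 13 × 14/2 = 91 covariance parameters from 20 subjects. Baseline-by-visit adds 13 fixed effects, and baseline as a first response makes 105 covariance parameters. Either could push the fit to the compound-symmetry fallback. This rules out the larger remedies but not one extra coefficient.

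One might also infer that adjustment improves precision whatever the dropout pattern, or that antigenic AAT and Z-polymer need the same change. Neither is supported: RMSE is sometimes slightly higher, and SAP 9.3.2 now only summarizes those two endpoints descriptively.

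**Conclusion.** The point holds in a limited form. The visible primary model conditions on observed changes only, which is narrower than Protocol 12.3.3.4 states. It would be too strong to say that the model breaks missing at random, because that is an assumption about the dropout process, not a property of a model.

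Under the planning values any bias from early loss of low-baseline subjects is upward. It runs from about +0.2 µM (at +2) or +0.5 µM (at +7) in the extreme case down to +0.1 µM or less with spread exits, and is nil under random dropout. The direction rests on the planned correlation of 0.8. The size rests on the assumed inter-visit correlation and dropout mechanism.

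Whether the final analysis includes baseline, or is run at all, cannot be seen in SAP 9.3.1. Dosing stopped on 25 September 2023 by sponsor decision, so missing Week 48 values may be largely administrative. The practical effect in this study may therefore be limited.

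**What to change.** In Protocol 12.3.3.1 and the matching SAP text:
- Add baseline functional AAT as a single main-effect covariate, with no baseline-by-visit term.
- Estimate the Week 48 change at the mean baseline of all FAS subjects, so that a subject with no post-baseline sample still contributes a baseline.
- Add the sampling variance of that mean (slope² × baseline variance/number in the FAS) to the model variance, so that the CI stays unconditional.
- State in 12.3.3.4 that missingness is assumed random given baseline and the observed changes.

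The cost is one parameter, a few lines of programming and no new data. In some later-dropout scenarios RMSE is unchanged or up to about 4% higher. A single slope is an approximation if the dependence on baseline differs between visits; that is acceptable with 20 subjects. If the covariate is not added, 12.3.3.4 should at least say that the assumption conditions on observed changes only.

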### 5.2 Study Rationale

The purpose of this study is to evaluate the efficacy and safety of VX-864 in individuals with the PiZZ genotype. VX-864 is theorized to prevent intracellular Z-AAT protein polymerization and increase secretion of functionally active AAT, potentially addressing unmet medical need in this population. Clinical data in individuals with the PiZZ genotype in the Phase 1 study VX21-864-008 and in the Phase 2 study VX19-864-101 demonstrate that VX-864 is generally safe and well tolerated in generally healthy subjects with the PiZZ genotype (refer to the VX-864 IB).

A small but statistically significant increase in blood levels of functional and antigenic AAT was demonstrated in the Phase 2 study VX19-864-101 over 28 days in subjects with the PiZZ genotype. In addition, in generally healthy subjects with the PiZZ genotype receiving multiple doses of VX-864 over 14 days in the recently completed Phase 1 open-label study VX21-864-008, evaluation of the concentration of VX-864 in the liver demonstrated adequate levels of study drug were distributed effectively to the target organ. The results of these 14-day and 28-day studies suggest further evaluation of VX-864 over a longer period is warranted, with the hypothesis that a longer period of VX-864 dosing may result in higher blood levels of functional and antigenic AAT compared with 28 days of dosing. The study results may also

inform future development of potential new small molecules in AATD. Hence, this study will evaluate VX-864 over a longer period than prior studies, i.e., 48 weeks in subjects with the PiZZ genotype.

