## 9.10 Replacement of Subjects

Subjects who withdraw or are withdrawn for nonsafety reasons during the study drug treatment period may be replaced at Vertex's discretion.

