7.4 Replacement

Subjects who withdraw or are withdrawn for non-safety reasons during the study drug treatment period may be replaced at Vertex's discretion. Refer to Section 9.10 of the CSP for more details.

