9.3.2 Analysis of Secondary Efficacy Variables

In this analysis, if the measured functional AAT levels are below the lower limit of quantification (LLOQ) of 2.77 μ M, the LLOQ value will be imputed for analysis purposes; if the measured functional AAT levels are above the upper limit of quantification (ULOQ) of 25.6 μ M, the ULOQ value will be imputed for analysis purposes.

If the measured antigenic AAT levels are below the LLOQ of 2.63 μ M, the LLOQ value will be imputed for analysis purposes; if the measured antigenic AAT levels are above the ULOQ of 45 μ M, the ULOQ value will be imputed for analysis purposes.

If the measured blood Z-polymer levels are below the LLOQ of 0.469 mg/L, the LLOQ value will be imputed for analysis purposes; if the measured blood Z-polymer levels are above the ULOQ of 2000 mg/L, the ULOQ value will be imputed for analysis purposes.

If the measured liver Z-polymer levels are below the LLOQ, the LLOQ value will be imputed for analysis purposes; if the measured liver Z-polymer levels are above the ULOQ of, the ULOQ value will be imputed for analysis purposes.

	Percent Stain Area: (unit = %)	H-Score: (unit = none)	Globule Density: (unit = number of globules/mm ²)
LLOQ	0.000%	0	0
ULOQ	100.000%	300	1000000

According to CSP (V2.0), “*There will be no further screening or enrollment, and no further study drug dosing, based on Sponsor decision to stop dosing in this study as of 25 September 2023.*” No subjects have had any post-treatment liver biopsy. The secondary endpoints related to liver Z-polymer will not be analyzed.

The observed values and change from baseline of the other secondary endpoints (functional AAT, antigenic AAT, and blood Z-polymer) will be summarized descriptively by group and overall at each visit.

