3. For efficacy assessments, the analysis visit window for Day 1, Day 7, Day 15, Day 21, Day 28, Wk 6, Wk 8, Wk 12, Wk 16, Wk 20, Wk 24, Wk 32, Wk 40 and Wk 48 will only be implemented for the assessments conducted on or before 1 day after the last dose of study drug. For safety assessments, the analysis visit window Day 1, Day 7, Day 15, Day 21, Day 28, Wk 6, Wk 8, Wk 12, Wk 16, Wk 20, Wk 24, Wk 32, Wk 40 and Wk 48 will only be implemented for the assessments conducted on or before 2 days after the day of last dose of study drug.
4. The analysis visit windows will be applied using the following rules for both scheduled and unscheduled visits:
 - If no measurement is available within a visit window, the measurement will be considered missing for the visit.
 - If there is more than 1 numerical measurement available within a visit window, use the following rules:
 - The measurement closest to the target day will be used.
 - If there are multiple measurements with the same distance from the target day, the latest measurement will be used.
 - Except for ECGs, if two measurements (one scheduled and one unscheduled) occur on the same day, the scheduled assessment will be used.

- For ECGs, if multiple ECG triplicates are obtained on the same day during the TE period, the mean of the ECGs on that day will be used as the ECG value on that day for summary purpose.

5. For measurements collected on the date of first dose of study drug, if it cannot be determined whether the measurement is before or after the first dose:
 - If a scheduled measurement is pre-dose in CSP, it will be treated as a pre-dose observation. If a scheduled measurement is post-dose in CSP, it will be treated as a post-dose observation.
 - Unscheduled measurements will be treated as post-dose observations.
6. The analysis visit windows will be implemented in the following order:
 - Step 1: The analysis visit window “Use nominal visit” is implemented. The nominal visits used in this step will be excluded in the next step.
 - Step 2: The other analysis visit windows are implemented.

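### The primary model's only visible fallback, compound symmetry, assumes equal variance at every visit, against the protocol's own constant-CV assumption; if it is used while AAT is still rising, the Week 48 interval is too narrow

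*Protocol*

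**What the plan says.** Protocol 12.3.3.1 models change from baseline in functional AAT with visit as the fixed effect, REML, Kenward-Roger degrees of freedom and an unstructured covariance. The Week 48 estimate, with its 95% CI and P value, is the primary result. The one contingency is: "If the model estimation does not converge, a compound symmetry covariance structure will be used instead". No heterogeneous structure and no robust variance is named.

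The Synopsis (Statistical Analyses) sizes the study on the width of that CI and assumes that "post-baseline blood levels of functional AAT have a constant coefficient of variation of 0.25". It also says: "To account for up to a 20% dropout rate, 20 subjects will be enrolled". Section 5.2 states, as what the study expects: "a longer period of VX-864 dosing may result in higher blood levels of functional and antigenic AAT compared with 28 days of dosing".

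SAP Appendix A lists 13 on-treatment efficacy visits after baseline. Its note 3 says that these windows "will only be implemented for the assessments conducted on or before 1 day after the last dose of study drug", so a subject who stops early supplies no Week 48 value. Protocol 9.10 and SAP 7.4 allow replacement of non-safety withdrawals at the sponsor's discretion.

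Dosing stopped on 25 September 2023. SAP 9.3.1, on the primary analysis, is redacted. SAP 9.3.2 says that the secondary blood endpoints "will be summarized descriptively by group and overall at each visit", and that no subject had a post-treatment liver biopsy.

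**The concern.** Under a constant coefficient of variation the SD of AAT grows with its mean. If AAT keeps rising, Week 48 has the largest variance of all visits. Homogeneous compound symmetry (the ordinary meaning of the term; the protocol does not use the word homogeneous) replaces that variance with an average over visits. Kenward-Roger is model-based and does not repair a wrong variance structure. The reported interval would then look more precise than the sizing calculation says it should be, as an artefact of the fallback. A continuing rise is the case that a 48-week study is meant to look for, although Section 5.2 says only that it may occur.

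**Working it through.** **Inputs from the Synopsis.** Baseline mean 4.1 µM, SD 0.6; post-baseline CV 0.25; correlation 0.8 between baseline and post-baseline; 16 evaluable of 20 enrolled; Week 48 change d from 2 to 7 µM.

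**Reproducing the plan's figure.** With s = 0.25 × (4.1 + d), the variance of change is 0.6² + s² − 2 × 0.8 × 0.6 × s.
- d = 2: s = 1.525, variance 1.222, SD 1.105; half-width t(0.975, 15) × 1.105/√16 = 0.59.
- d = 7: s = 2.775, variance 5.397, SD 2.323; half-width 1.24.

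Both match the Synopsis.

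**What compound symmetry does.** With complete data and visit as the only fixed effect, the REML compound-symmetry variance at every visit is the average of the 13 visit-specific variances. The Week 48 standard error is therefore multiplied by √(mean variance / Week 48 variance). For a straight-line rise this is √(0.669/1.222) = 0.740 at 2 µM and √(1.745/5.397) = 0.569 at 7 µM.

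**Assumptions not in the documents.** The time course, with each profile scaled to reach d at Week 48, and a correlation of 0.8 between post-baseline visits (the protocol gives 0.8 for baseline against post-baseline only).

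**Coverage.** Simulated REML fits with Kenward-Roger, random monotone dropout, 20 enrolled and 13 at Week 48, 800 runs per cell (95% simulation error about 1.5 to 3 points):

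| Profile | SD ratio, 2 µM | SD ratio, 7 µM | Coverage, 2 µM | Coverage, 7 µM |
|---|---|---|---|---|
| Straight line over 48 weeks | 0.740 | 0.569 | 84.0% | 69.5% |
| 12-week time constant | 0.840 | 0.738 | 89.0% | 82.3% |
| 4-week time constant | 0.921 | 0.871 | 92.0% | 88.7% |
| 1-week half-time | 0.971 | 0.952 | 94.1% | 93.0% |
| Flat from Day 7 | 1.000 | 1.000 | 95.4% | 95.0% |
| Peak of 1.5 × d at Day 28, then falling | 1.087 | 1.159 | 96.9% | 97.5% |

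Heterogeneous compound symmetry covered 95-96% in every profile, and all its fits converged. A separate check with 16 complete subjects (20,000 runs, Satterthwaite degrees of freedom) gave homogeneous compound-symmetry coverage of 86/90/93/95% at 2 µM and 74/86/91/95% at 7 µM for straight-line / 12-week / 4-week / flat. With 16 complete subjects, a post-baseline correlation of 0.9 or serially decaying correlations moved coverage by about 1 point.

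**No change at any visit.** The mean, and so the variance, is then the same at all post-baseline visits. Compound symmetry rejected in 5.0% of 3,000 runs (20 enrolled, 13 at Week 48).

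**When the fallback is reached.** Thirteen visits give 13 × 14/2 = 91 covariance parameters. Regressing Week 48 on the 12 earlier visits uses 13 coefficients, so residual degrees of freedom are 3, 2, 1 and 0 with 16, 15, 14 and 13 Week 48 values. Failure of the unstructured fit is therefore shown only at 13 or fewer. At the planning stage, P(13 or fewer completers) with 0 / 2 / 4 replacements is 9 / 2 / 0.4% at the planned 20% loss and 39 / 19 / 7% at an assumed 30% loss.

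**After the dosing stop.** Every Group B subject was due a second biopsy at Week 24 (Cohort B1) or Week 48 (Cohort B2). If none took place, and unless biopsies were skipped, no B1 subject reached Week 24 and no B2 subject reached Week 48. Week 48 values could then come only from Group A, about 10 subjects. That is fewer than 13, so a 13-visit unstructured fit could not be supported.

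**The case against.** The strongest objection is that this may never matter. The cells with 13 of 20 or 16 complete subjects at Week 48 are not what this trial appears to have produced, so neither their coverage figures nor the planning-stage trigger probabilities describe it. The secondary blood endpoints have become descriptive, and the redacted SAP 9.3.1 opens with the same reference to the amended protocol that introduces the dosing stop in 9.3.2. The model may already have been dropped. All of this stands and sets the priority. It also works the other way: with about 10 Week 48 values, anyone who did run the model would need the fallback.

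Second, the documents give no time course, and the error can go in either direction. This also stands. The largest losses need a straight-line rise over 48 weeks, and the 70% figure also needs the largest change considered.

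Third, the conclusion about any effect would not change. At 2 µM the interval is about ±0.40 against ±0.58 for the straight-line rise, and at 7 µM about ±0.62 against ±1.18. All exclude zero, and the documents set no threshold for the interval. That is correct; what is affected is the stated precision, which is the quantity the study was sized on.

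A reader might infer that the fallback inflates type I error. It does not when there is no change at any visit. A reader might also infer that the unstructured model would fail at the planned 16 completers. That has not been shown, and inclusion of all 13 visits is itself read from the SAP windows, since Protocol 12.3.3.1 lists none.

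**Conclusion.** The inconsistency is real. The protocol's variance assumption and its only visible fallback agree only when mean AAT is the same at all post-baseline visits. Three conditions must hold before the Week 48 interval is too narrow: the model is run, the fallback is used, and AAT is still rising after the early visits. For rises with a 12-week to 4-week time constant, coverage is then about 89-92% at 2 µM and 82-89% at 7 µM; 84% and 70% are a worst case. These figures are illustrative. They rest on the assumed time course and post-baseline correlation, and on more Week 48 data than the trial probably has.

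It would be tempting to conclude that the reported primary result is unreliable. The documents do not support that: they do not show that the model was run, and the relevant SAP text is blacked out. This is a minor point of the lowest priority.

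**What to change.** If the repeated-measures model is retained, replace the fallback with heterogeneous compound symmetry (13 variances and one correlation, 14 parameters), keeping Kenward-Roger. If that does not converge, report a paired t interval at Week 48. Label it completers-only, because it does not use the missing-at-random assumption of Protocol 12.3.3.4. In the illustration with 13 completers the paired t interval covered about 95%, with half-widths of 0.66 at 2 µM and 1.38 at 7 µM. If the redacted SAP text already drops the model, nothing needs changing.

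The change is wording only. The cost is a wider interval when the fallback is used. With 13 completers and a rising profile, the mean half-width is about 0.58 instead of 0.40-0.53 at 2 µM, and about 1.18 instead of 0.62-1.06 at 7 µM. If AAT is flat from Day 7 the cost is small: 0.58 against 0.55 at 2 µM.
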